4.4. Tertiary/Exploratory Endpoint(s) Analyses

There are no tertiary/exploratory endpoints in this study.

4.5. Safety Analyses

The analyses will be descriptive and conducted on the ES.

The following calculations will be performed for each group:

- The percentage of doses and participants reporting at least 1 AE (solicited or unsolicited) during the 14-day (Day 1 to Day 14) solicited follow-up period will be computed, along with exact 95% CI. The same calculations will be done for AEs (solicited or unsolicited) rated as grade 3 in intensity and for AEs leading to a medically attended visit.
- The percentage of doses over the study and the percentage of participants (by dose and over the study) reporting each individual solicited systemic event will be computed, over the 14-day (Day 1 to Day 14) solicited follow-up period, following study intervention administration, along with exact 95% CI. The same calculations will be done for each individual solicited systemic event rated as grade 3 (grade 3 or grade 4 for fever) in intensity and events leading to a medically attended visit. Temperature above specific thresholds will also be summarized with threshold defined by half degree increment.

Note: Intensity of fever will be assessed by considering the grading scales recommended by the Chinese authorities [NMPA, 2019].

- The verbatim reports of unsolicited AEs will be reviewed by a physician and will be coded according to MedDRA. Every verbatim term will be matched with the appropriate Preferred Term. The percentage of participants with unsolicited AEs occurring within 31-day (Day 1 to Day 31) follow-up period after any dose of *Rotarix* PCV-free with its exact 95% CI will be tabulated by Preferred Term. The same calculations will be done for each AE rated as grade 3 in intensity, for AEs leading to a medically attended visit and for AEs causally related to HRV as per the investigator assessment.
- The percentage of participants reporting the occurrence of SAEs (any, related, fatal, fatal related) from Dose 1 of the study intervention up to study end with its exact 95% CI will be tabulated by study group and by preferred term.
- The percentage of participants reporting the occurrence of SAEs (any, related, fatal, fatal related) within 31-day (Day 1 to Day 31) follow-up period after any dose with its exact 95% CI will be tabulated by study group and by preferred term.
- SAEs and dropouts due to AEs will be described in detail.

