4.2. Scientific rationale for study design

In China, under the NIP, a 3-dose primary vaccination against poliovirus is currently recommended during the first year of life in a 2, 3 and 4 months of age schedule. *Rotarix* should be given in a 2-dose schedule between 6-24 weeks of age with an interval of at least 4 weeks between doses. Till date, there is no data available on the immunogenicity and safety of IPV when co-administered with *Rotarix* PCV-free, in healthy Chinese infants.

The current study is therefore designed to assess the immunogenicity and safety of IPV when it is co-administered with *Rotarix* PCV-free, compared to administration of the vaccines separately. There are 2 parallel arms:

- **Co-administration group:** participants will receive *Rotarix* PCV-free co-administered with IPV at Month 0.5 and Month 1.5, and IPV at Month 2.5.
- **Staggered group:** participants will receive *Rotarix* PCV-free at Day 1 and Month 1, and IPV at Month 0.5, Month 1.5, and Month 2.5.

The study will enroll infants 6-10 weeks of age. This will ensure compliance with the recommendations mentioned below, including for participants of the Co-administration group who will receive the first dose of *Rotarix* and IPV at 2 weeks after enrolment:

- As per CDC recommendation, the first dose of *Rotarix* should be given before an infant is 15 weeks of age and the second dose before they turn 8 months old.
- As per EU SmPC recommendation, the first dose of *Rotarix* may be administered from 6 weeks of age. There should be an interval of at least 4 weeks between doses. The second dose should preferably be given before 16 weeks of age but must be completed by the age of 24 weeks.
- In China, IPV is recommended as 2 doses at the age of 2 and 3 months and no later than 13 weeks of age for the first dose.

Please refer to the IB for further information on *Rotarix*.

Please refer to the PI for further information on Beijing Biological Products Institute Co.,Ltd. IPV.

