10.3.3. Solicited events

Definition of solicited event

- Solicited events are predefined events-administration site events and systemic events for which the participant's parent(s) /LAR(s) is specifically questioned, and which are noted by the participant's parent(s) /LAR(s)] in their diary/eDiary.

Note: for this study solicited systemic events will be collected post Dose 1 and Dose 2 of study interventions administration.

The following events will be solicited:

Table 17 Solicited systemic events

Fever
Diarrhea
Vomiting
Irritability/Fussiness
Loss of appetite
Cough/runny nose

Note: participants' parent(s)/LAR(s) will be instructed to measure and record the body temperature in the evening. Should additional temperature measurements be performed at other times of day, participants' parent(s)/LAR(s) will be instructed to record the highest temperature in the diary card.

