10.3.7.3. Medically attended visits

For each solicited (post administration of Dose 1 and Dose 2 of *Rotarix* and IPV) and unsolicited symptom (post *Rotarix* administration) the participant experiences, the participant's parent(s)/LAR(s) will be asked if the participant received medical attention defined as hospitalization, or an otherwise unscheduled visit to or from medical personnel for any reason, including emergency room visits. This information will be recorded in the eCRF.

Medical attention received for SAEs will have to be reported using the normal AE reporting process in the eCRF.

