
 To evaluate the reactogenicity of Rotarix PCV-free and IPV in terms of solicited systemic events. To assess the safety of Rotarix PCV-free in terms of unsolicited AEs and serious adverse events (SAEs) and safety of IPV in terms of SAEs. 	
 Solicited AEs 
 For each solicited systemic event, percentage of participants reporting the occurrence of the event within 14 days (Day 1- Day 14) after Dose 1 and Dose 2 of Rotarix and IPV Unsolicited AEs 
 Percentage of participants reporting the occurrence of unsolicited AEs within 31 days (Day 1- Day 31) after each dose of Rotarix, according to the MedDRA classification. SAEs: 
 Percentage of participants reporting SAEs from the first dose of the study intervention up to study end in the Co-administration and Staggered groups.

Ab: Antibody; GMC: Geometric mean Ab concentration; GMT: Geometric mean Ab titer; IgA: Immunoglobulin A; IPV: Inactivated poliovirus vaccine; MedDRA: Medical Dictionary for Regulatory Activities; mL: milliliter; PCV: *Porcine circovirus*; SAE: Serious Adverse Event; U: Unit

*Seroconversion rate for IPV neutralizing Ab is defined as percentage of participants with

[figure not shown]
- Titer $\geq 1:8$ at 1 month after 3 dose primary schedule of IPV in participants with titer $<1:8$ pre-vaccination
- Titer ≥ 4 -fold increase in titer 1 month after 3 dose primary vaccination schedule in participants with titer $\geq 1:8$ pre-vaccination.

Note: the 4-fold increase will take into consideration the expected decline in maternal antibodies with estimated half-life of 28 days.

**Seroconversion rate for anti-RV IgA Ab is defined as the percentage of participants who were initially seronegative (i.e., with anti-RV IgA Ab concentration <20 U/mL prior the first dose of *Rotarix*) and developed anti-RV IgA Ab concentration ≥ 20 U/mL at 1 month post Dose 2.

** complementary details on estimand including impact of intercurrent events on the analysis is available in Section 3 and Section 4.

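### The over-the-study solicited-event row in SAP 4.5 covers 28 diary days per infant in Co-administration and 56 in Staggered, so it is not like-for-like and can mask a higher per-visit rate

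*SAP*

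**What the plan says.** SAP 1.1 defines the solicited endpoint, for each event, at participant level: the "percentage of participants reporting the occurrence of the event within 14 days (Day 1- Day 14) after Dose 1 and Dose 2 of" both vaccines. Protocol 10.3.3 confirms that "for this study solicited systemic events will be collected post Dose 1 and Dose 2 of study interventions administration", and Protocol 10.3.7.3 names both vaccines ("post administration of Dose 1 and Dose 2 of *Rotarix* and IPV"). IPV Dose 3 has no solicited follow-up.

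Protocol 4.2 sets the visits. Co-administration infants receive Rotarix "PCV-free co-administered with IPV at Month 0.5 and Month 1.5, and IPV at Month 2.5". Staggered infants receive Rotarix at Day 1 and Month 1, and IPV at Months 0.5, 1.5 and 2.5. The Schedules of Activities agree: diary cards go out at two visits in Table 1 and at four in Table 2.

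SAP 4.5 plans, for each group, three summaries of each solicited event: a percentage of doses, a percentage of participants by dose, and a percentage of participants over the study. On the two participant summaries it says that "the percentage of participants (by dose and over the study) reporting each individual solicited systemic event will be computed". Grade 3 and medically attended events get the same calculations. SAP 6.2.8 counts an event once per period, however many days it lasts. The over-the-study percentage carries no adjustment or caveat for the number of windows.

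**The concern.** The two groups are solicited for different lengths of time. Fever, runny nose, irritability and loose stools occur in infants of this age without any vaccine, and each extra window is another chance to record one. An any-window percentage therefore rises with the number of windows, and Staggered has twice as many.

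Protocol 4.2 says the study assesses co-administration against giving the vaccines separately, so readers will set the two columns side by side. On this row the imbalance favours Co-administration, so a moderately higher reaction rate per joint visit could appear as a lower percentage. Protocol 9.3.2 recognises a related difficulty for anti-rotavirus IgA: it declines to compute group differences because the Rotarix schedules differ. The reactogenicity tables have no such safeguard.

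**Working it through.** **Inputs.** Windows per infant: 2 in Co-administration, 4 in Staggered (Protocol 4.2, 10.3.3, 10.3.7.3). Window length: 14 days (SAP 1.1). The documents give no solicited-event rate and no within-infant correlation, so the per-window risk *p* (5% to 30%) and the correlation ρ are assumptions. The plan states no figure of its own for solicited events; its only power figures concern seroconversion.

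**Solicited days.** Co-administration: 2 × 14 = 28. Staggered on the optimal schedule: 4 × 14 = 56. For overlap, use the allowed intervals in SAP Table 5. Visit 1 to 2 is at least 14 days, so the first two windows do not overlap. Visit 2 to 3 can be as short as 28 − 18 = 10 days (4 days of overlap), and Visit 3 to 4 as short as 14 + 28 − 36 = 6 days (8 days of overlap). These two gaps sum to at least 28 days, so both cannot be short together. The range is therefore 56 − 8 = 48 to 56 days.

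**Equal risk, independent windows.** Co-administration shows 1 − (1 − p)², Staggered 1 − (1 − p)⁴. The Co-administration risk *q* at which the rows agree solves (1 − q)² = (1 − p)⁴, so q = 1 − (1 − p)² and q/p = 2 − p.

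| p | Co-administration | Staggered | Gap (points) | Break-even q/p |
|---|---|---|---|---|
| 5% | 9.8% | 18.5% | 8.8 | 1.95 |
| 10% | 19.0% | 34.4% | 15.4 | 1.90 |
| 20% | 36.0% | 59.0% | 23.0 | 1.80 |
| 30% | 51.0% | 76.0% | 25.0 | 1.70 |

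Example: Staggered 10% per window, Co-administration 15%. The row shows 1 − 0.85² = 27.8% v 34.4%, lower in the group with the higher rate.

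**Correlated windows.** Under a beta-binomial with a = p(1 − ρ)/ρ and b = (1 − p)(1 − ρ)/ρ, the chance of no event in k windows is the product of (b + j)/(a + b + j) for j = 0 to k − 1. At p = 10% and ρ = 0.2, a = 0.4 and b = 3.6:

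- Two windows: (3.6/4)(4.6/5) = 0.828, so 17.2%.
- Four windows: 0.828 × (5.6/6)(6.6/7) = 0.729, so 27.1%.

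At ρ = 0.2 the figures are 8.8% v 14.4% for p = 5% and 32.8% v 48.4% for p = 20%. At ρ = 0.5 and p = 10% they are 14.5% v 19.4%. Break-even ratios for p from 5% to 30% run from 1.55 down to 1.42 at ρ = 0.3, and from 1.37 down to 1.29 at ρ = 0.5.

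**Vaccine effects only, no background.** If each vaccine independently carries 10%, a joint visit carries 1 − 0.9 × 0.9 = 19%. Over the study, Co-administration shows 1 − 0.81² = 34.4% and Staggered 1 − 0.9⁴ = 34.4%: no gap.

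**Vaccine effects plus background.** Add 5% background per window. Co-administration shows 1 − (0.9 × 0.9 × 0.95)² = 40.8% and Staggered 1 − (0.9 × 0.95)⁴ = 46.6%. The gap returns with no interaction between the vaccines.

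**The case against.** The strongest reply is that nothing is concealed. The SAP sentence opens "The percentage of doses over the study and the percentage of participants (by dose and over the study", so two of its three displays do not accumulate over windows. With 19% per window in Co-administration and 10% in Staggered, the over-the-study rows would agree, but the percentage of doses would show 19% v 10%. A reader might infer from the 28 v 56 day imbalance that extra reactogenicity is hidden throughout the output. The documents do not support that.

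Safety is also descriptive ("The analyses will be descriptive and conducted on the ES"), Protocol 9.4.1 presents it as a within-group assessment, and no between-group safety difference is planned. No formal conclusion depends on this row. That stands, and it limits the weight of the point.

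The row can also be defended as the burden of each whole schedule. That holds only in part, because Co-administration infants are not solicited outside their 28 days and background illness is collected for up to twice as long in Staggered. The additive case does give equal figures, but only with no background.

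The other displays do not fully repair the row. The endpoint is by participant. The percentage of doses pools Rotarix-only and IPV-only visits in Staggered. The SAP's only definition of a dose (6.1.5, for dose counts) is a vaccination visit. On that reading Staggered Dose 1 is Rotarix alone and Dose 2 is IPV alone, while each of the first two Co-administration doses is both vaccines, so by-dose rows do not line up.

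**Conclusion.** The point holds for the over-the-study participant percentage. It covers 28 v 56 days (48 to 56 with permitted overlap). With background symptoms and equal per-window risk, it understates Co-administration relative to Staggered by construction. For assumed risks of 5% to 30% and independent windows the gap is 8.8 to 25.0 points, and the Co-administration rate per window would have to reach about 1.7 to 1.95 times the Staggered rate before the row showed parity. At correlation 0.5 that falls to about 1.3 to 1.4 times. The direction follows from the design; the size rests on assumed rates and correlation.

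Three stronger readings are not supported. The imbalance does not affect all reactogenicity output, because the percentage of doses would still show a per-window difference. It does not touch the confirmatory immunogenicity objective. The participant rows for at least one AE share it only if they are pooled over doses, which the SAP does not say.

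**What to change.** In SAP 4.5 and the table shells:

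- Keep the total row and footnote it: *28 v 56 solicited days; not like-for-like between groups*. Deleting it would lose the schedule-level figure.
- Add two participant-level rows with two windows in each group: event in Days 1–14 after either Rotarix dose, and event in Days 1–14 after IPV Dose 1 or 2. In Co-administration both rows use the same visits.
- Footnote these rows to say that Co-administration windows follow both vaccines and Staggered windows follow one. They equalise time, not exposure: in the no-background example above each would show 34.4% v 19.0% with no interaction.
- State that by-dose means by vaccine and dose number, so that rows align between groups.
- Do the same for the Grade 3 and medically attended rows, and for the at-least-one-AE participant rows if they are pooled over doses.

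This needs SAP wording and table shells only, and no new data. The downside is a few extra table rows.

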4.6. Other Analyses

Not applicable.

4.7. Interim Analyses

No interim analysis is planned. All analyses will be conducted on final data and therefore no statistical adjustment for interim analyses is required.

The final analysis will include all data up to one month after the third dose of IPV. These analyses will include the final analysis of immunogenicity and the final analysis of solicited and unsolicited symptoms and SAEs from the first dose up to Visit 7.

4.8. Changes to Protocol Defined Analyses

There were no changes or deviations to the originally planned statistical analysis specified in the protocol amendment 1 (Dated: 25 October 2023).

5. SAMPLE SIZE DETERMINATION

A maximum of 400 participants (200 in the Co-administration group and 200 in the Staggered group) will be randomized such that approximately 160 evaluable participants complete the study, in each group for the evaluation of the primary objective assuming that approximately 20% of the enrolled participants will not be evaluable.

Participants who withdraw from the study will not be replaced.

The power presented in [Table 3](#) is based on PASS 2019 (one-sided Non-Inferiority Tests for the Difference Between Two Proportions), under the alternative hypothesis of a 96.23% (Polio 1), 93.83% (Polio 2), and 97.60% (Polio 3) seroconversion rate for the Staggered group and a true difference of 0% between the Co-administration group and Staggered group, using Miettinen and Nurminen's Likelihood Score Test of the Difference. Under these conservative assumptions the overall power is above 90.4% (i.e., global type II error is conservatively computed as the sum of nominal type II errors).

Table 3 Probability that the lower limit of the 95% CI around group difference in the percentage of participants with anti-poliovirus types 1, 2 and 3 antibody seroconversion 1 month post Dose 3 of IPV (Co-administration group minus Staggered group) is greater than or equal to -10%

Ag	True seroconversion rate (Co-administration group) *	True seroconversion rate (Staggered group)*	N evaluable (each group)	Power	Alpha
Polio 1	96.23%	96.23%	160	98.2%	0.025
Polio 2	93.83%	93.83%	160	92.5%	0.025
Polio 3	97.60%	97.60%	160	99.7%	0.025
Overall				90.4%	

Ag: Antigen; N: number of participants

* Observed positive conversion rate from the Beijing Biological Products Institute Co.,Ltd. IPV package insert
[Inactivated Poliomyelitis Vaccine Made From Sabin Strains (Vero Cells) package insert, 2019].

6. SUPPORTING DOCUMENTATION

6.1. Appendix 1 Study Population Analyses

As per EudraCT reporting requirement, a summary of number of participants enrolled by country and by age category will be provided for the enrolled set.

6.1.1. Participant Disposition

Number of enrolled participants and reason for exclusion from ES will be described by group.

Number of vaccinated participants and reason for withdrawal from the study will be described by group for the ES.

The distribution of participants enrolled in each site will be tabulated across and per study group for the ES.

Number of ES participants excluded from PPS analyses will be tabulated for each group based on the reason for exclusion.

6.1.2. Demographic and Baseline Characteristics

The demography and baseline characteristic summaries will be provided for both ES and PPS.

The median, mean, range and standard deviation of age (in weeks) for each dose of study intervention and for gestational age (in weeks) will be computed by group. Median, mean and standard deviation of height in centimeter and weight in kilogram at Visit 1 will be computed by group. The study sites, geographical ancestry and sex composition will be presented by group.

6.1.3. Protocol Deviations

Important protocol deviations will be summarized.

Protocol deviations will be tracked by the study team throughout the conduct of the study. These protocol deviations will be reviewed to identify those considered as important as follows:

- Data will be reviewed prior to freezing the database to ensure all important deviations (where possible without knowing the study intervention details) are captured and categorized in the protocol deviations dataset.
- This dataset will be the basis for the summaries of important protocol deviations.

Protocol deviations which result in exclusion from the analysis set will also be summarized.

- Data will be reviewed prior to freezing the database to ensure all deviations leading to analysis population exclusions are captured and categorized in the protocol deviations ADaM dataset (note these exclusions are not captured in the SDTM dataset).

The following deviations will be considered important protocol deviations.

Codes 800, 900 and 1030 will lead to elimination from the ES and the PPS. The other codes are specific to the PPS. Refer to Section 3 for the summary of protocol deviation leading to elimination from analysis set.

Code	Decode: Condition under which the code is used
800	Fraudulent data
900	Invalid informed consent
1030	Study vaccine dose not administered but participant number allocated: participants enrolled but not vaccinated
1050	Randomization failure: forced or manual randomization*. First dose of vaccine administration not aligned with the randomized treatment.
1040	Administration of concomitant vaccine(s) forbidden in the protocol: Administration of a non-study vaccine (HRV/IPV) or non-routine vaccine starting from 30 days before the first vaccination up to Visit 7 blood sample.
1060	Randomization code broken at the investigator site: Participants unblinded in the central randomization system or unblinding reported as protocol deviation
1070	Study vaccine dose not administered according to protocol: 
 • Participant who did not receive the complete dose of each of the study vaccines (two doses for HRV PCV-free and three doses for IPV). • Route of study vaccine administration wrong or unknown.
1080	Vaccine temperature deviation: Participants who have received a vaccine which had a temperature deviation qualified as inappropriate for use by Quality Assurance.
1090	Expired vaccine administered: Participants who received an expired vaccine
2010	Protocol violation linked to the inclusion/exclusion criteria: Ineligible participants who was vaccinated. (Refer to protocol Section 5 “Study population” for the exhaustive list of inclusion/exclusion criteria).
2020	Anti-RV IgA antibody concentration at pre-vaccination above or equal to 20 U/mL or initially unknown antibody status
2040	Administration of any medication from day 1 to the Visit 7 blood sample which is forbidden by the protocol (see Section 5.2 from the protocol)
2070	Concomitant infection not related to the vaccine which may influence immune response => who have concomitant infection up to Visit 7 blood sample, which may influence the immune system namely RV gastroenteritis, immunosuppressive or immunodeficient conditions identified before Visit 7.

Code	Decode: Condition under which the code is used
2080	Non-compliance with vaccination schedule (including wrong and unknown dates) for IPV and/or HPV PCV-free
2090	Non-compliance with the blood sampling schedule (including wrong and unknown dates)
2100	Serological results not available 1 month post Dose 2 for Rotarix PCV-free and 1 month post Dose 3 for IPV.
2120	Obvious incoherence/abnormality or error in data

- * Forced randomization: In case of supplies shortage for the next assigned vaccine according to the randomization schedule at the clinical site, the randomization system will use the forced randomization procedure in order to continue to enrol and vaccinate participants. The system moves seamlessly to the next treatment/randomization number for which vaccine supplies are available. The site will not be aware of the forced randomization event.
- *Manual randomization: In case the randomization system is unavailable, the investigator has the option to perform randomization by selecting supplies available at the site according to a pre-defined rule. In case the randomization system is available, a vaccine different from the randomized treatment may have been administered at dose 1.

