Distribution of 'Participant card'		0						See Section 8.3.5 for more information
Distribution of diary cards		●		●				
Laboratory Assessment								
Blood sampling for antibody determination (at least 2 mL)		● [▲]				● [▲]	●	^Blood sampling to be done before study intervention administration. Volume of the blood sample should be between 2 and 2.5 mL. See Section 8.1.1 for more information
Safety assessments								
Record any concomitant medications/vaccinations		●	●*	●	●*	●	●	See Section 6.8 for more information
Recording of solicited events post Dose 1 and Dose 2 of study intervention administration (Days 1-14*)		●		●				See Section 10.3.3 and Section 10.3.6.1 for more information
Recording of unsolicited AEs after each dose of Rotarix administration (Days 1-31)		●	●*	●	●*	●		See Section 10.3.4 and Section 10.3.6.1 for more information

CONFIDENTIAL

218485 (ROTA-098)
Protocol Amendment 1 Final

Age at time of study enrolment	6-10 weeks							Notes
	Visit 1	Visit 2	Visit 3 ^a	Visit 4	Visit 5 ^a	Visit 6	Visit 7	
Type of contact	Day 1	Month 0.5	Month 1	Month 1.5	Month 2	Month 2.5	Month 3.5	
Record any intercurrent medical conditions ^b		●	●*	●	●*	●	●	See Section 9 for more information
Recording of AEs that led to withdrawal from study	●	●	●*	●	●*	●	●	See Section 10.3.6.1 for more information.
Recording of SAEs	●	●	●*	●	●*	●	●	See Section 10.3.6.1 for more information
Recording of SAEs related to study participation, or to a concurrent GSK medication/vaccine	●	●	●*	●	●*	●	●	See Section 10.3.6.1 for more information. The collection and reporting periods start once the participants' parents/LARs informed consent is obtained
Return of diary cards				●		●		
Diary card transcription by investigator or designee				●		●	●	
Study Conclusion							●	See Section 4.4 for more information

AE: Adverse Event; IPV: Inactivated poliovirus vaccine; LAR: Legally Acceptable Representative; PCV: *Porcine circovirus*; PCV-free: no detection of PCV-1 and PCV-2 according to the limit of detection of the tests used; SAE: Serious Adverse Event; mL: milliliter

● is used to indicate a study procedure that requires documentation in the individual eCRF.

●* is used to indicate documentation activity that does not involve any site visit. These activities can be recorded by the participant and will be collected at the next site visit.

○ is used to indicate a study procedure that does not require documentation in the individual eCRF.

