3. ANALYSIS SETS

Table 2 Population for analyses

Analysis Set	Definition / Criteria	Analyses Evaluated
Screened	
 All participants who were screened for eligibility 	
 Study Population
Enrolled	
 All participants who entered the study (who were randomized or received study intervention or underwent a post-screening procedure) NOTE: screening failures (who never passed screening even if rescreened) and participants screened but never enrolled into the study (Met eligibility but not needed) are excluded from the Enrolled Analysis set as they did not enter the study. 	
 Study Population
Exposed	
 All participants who received at least one dose of any of the 2 study interventions. Participants will be analyzed according to the study intervention administered at dose 1. 	
 Safety
Per-Protocol (PP)	
All eligible participants from the exposed set who meet the following requirements:
 
 who received the study interventions according to their random assignment and the expected study intervention administration schedule and without intercurrent conditions* that may interfere with immunogenicity and without prohibited concomitant medication/vaccination. for anti-poliovirus types 1, 2 and 3 analyses at 1 month post Dose 3 of IPV, participants should have pre- and post-vaccination immunogenicity results for at least 1 antigen and should have complied with interval between IPV Dose 3 and the post IPV Dose 3 blood sample. for anti-RV IgA analyses at 1 month post Dose 2 of Rotarix PCV-free, participants should have pre- and post-vaccination immunogenicity results and should have complied with the interval between Rotarix Dose 2 and the post Rotarix PCV-free Dose 2 blood sample. 	
 The PP Set will be used for the immunogenicity analyses. If, in any study intervention group, the percentage of vaccinated participants with serological results excluded from the PP Set for analysis of immunogenicity is 5% or more, a second analysis based on the Exposed Set will be performed to complement the PP Set analysis.

* Immunosuppressive or immunodeficient conditions identified before Visit 7.

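### As written, the per-protocol set for anti-RV IgA excludes infants for events after their IgA sample was drawn; the effect is modest and limited to descriptive endpoints

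*SAP*

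**What the plan says.** SAP Section 3, Table 2 (and Protocol Table 15) defines one PPS. Its common conditions apply to both endpoints: study interventions received as randomised and on schedule, no prohibited concomitant product, and no immunosuppressive or immunodeficient condition identified before Visit 7. Two further bullets follow, one for polio and one for anti-RV IgA. The IgA bullet says that "participants should have pre- and post-vaccination immunogenicity results and should have complied with the interval between" Rotarix Dose 2 and the sample that follows it. It adds conditions and relaxes none of the common ones.

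SAP 6.1.3 turns this into codes: "Codes 800, 900 and 1030 will lead to elimination from the ES and the PPS. The other codes are specific to the PPS". No code is tied to an endpoint. The relevant ones are:
- **1070**: removes a "Participant who did not receive the complete dose of each of the study vaccines (two doses for HRV PCV-free and three doses for IPV").
- **1040**: forbidden vaccines "starting from 30 days before the first vaccination up to Visit 7 blood sample".
- **2040**: "Administration of any medication from day 1 to the Visit 7 blood sample which is forbidden by the protocol".
- **2070**: infants "who have concomitant infection up to Visit 7 blood sample, which may influence the immune system namely RV gastroenteritis" or an immune condition.
- **2080**: "Non-compliance with vaccination schedule (including wrong and unknown dates) for IPV and/or HPV PCV-free" (the second abbreviation is evidently a slip for HRV).
- **2090 and 2100**: blood-sampling schedule, and availability of the post-Rotarix and post-IPV serology, each written without separating the two endpoints.

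Protocol Table 10 places the post-Dose 2 IgA sample at Visit 5 (Month 2) in Staggered and Visit 6 (Month 2.5) in Co-administration. IPV Dose 3 is due at Visit 6 in both groups. For the Co-administration Visit 6 sample, Protocol Table 1 specifies: "Blood sampling to be done before study intervention administration".

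**The concern.** Once the post-Dose 2 IgA sample is drawn, the rotavirus endpoint is complete. A missed IPV Dose 3, a late IPV visit, or a forbidden product or infection after that draw cannot alter it. A programmer following the codes as written would still remove the infant from all three IgA endpoints (seroconversion, GMC, and the share at or above 90 U/mL).

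Two things are at stake. The first is avoidable loss of valid data. The second is selection on what happened after the outcome was measured. Most of the later events have no evident link to the IgA response, but rotavirus gastroenteritis under code 2070 may have one. Protocol 8.1.4 describes post-vaccination IgA seropositivity as a correlate of vaccine efficacy, so infants with rotavirus disease after the draw may more often be non-responders. Removing them could push the seroconversion estimate upward. The documents give no rate for such disease, so only a direction can be stated.

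**Working it through.** **1. Order of events on the optimal schedule** (SAP Tables 4 and 5; days from Visit 1)

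| | Staggered | Co-administration |
|---|---|---|
| Post-Dose 2 IgA sample | Visit 5: 30 + 30 = day 60 | Visit 6: 15 + 30 + 30 = day 75, before dosing |
| IPV Dose 3 | Visit 6: 15 + 30 + 30 = day 75 | Visit 6: day 75, after the draw |
| Polio sample | Visit 7: 75 + 30 = day 105 | Visit 7: 75 + 30 = day 105 |
| IgA sample to IPV Dose 3 | 15 days | 0 days |
| IgA sample to Visit 7 | 45 days | 30 days |

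With the allowed windows, the time from IgA sample to Visit 7 in Staggered runs from (14 + 28 + 28 + 30) − (36 + 36) = 28 days to (18 + 36 + 36 + 36) − (28 + 28) = 70 days. In Co-administration it is 30 to 36 days. The ranges overlap, so the longer period in Staggered describes the planned schedule, not every infant.

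**2. What each code can do after the IgA sample**
- 1070 needs a missed or incomplete dose. In Staggered it can act on IPV Dose 3, due about 15 days after the draw. In Co-administration that dose is due at the same visit, so an infant who attends for the draw has normally also received it.
- 2080 can act through the timing of IPV Dose 3.
- 1040, 2040 and 2070 need a forbidden product, an infection or an immune condition. A missed Visit 7 alone does not trigger them.
- The IgA bullet in SAP Table 2 requires no Visit 7 sample. A Visit 7 loss alone therefore removes an infant from the IgA set only if 2090 or 2100 is applied across endpoints.

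**3. Numbers affected by code 1070**

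The plan's own figure (SAP Section 5): 200 per group with about 20% non-evaluable gives 200 × 0.80 = 160 evaluable and 40 lost. That 160 is stated for the primary objective; the documents give no size for the IgA set. As an illustration, assume the 40 losses accrue evenly over 3.5 months and each loss between Visit 5 and Visit 6 means a missed IPV Dose 3.
- Staggered: 40 × 0.5/3.5 = 5.7, about 6 infants.
- Co-administration: 40 × 0/3.5 = 0, so almost none.

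Taking 160 as the set under the rule as written, Staggered would have about 160 + 6 = 166 without it.

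**4. Effect on precision** (Clopper-Pearson 95% CI; the seroconversion rate is assumed, since the documents give none for IgA)

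| Assumed rate | n = 160 | n = 166 | Ratio |
|---|---|---|---|
| 70% | 112/160: 14.72 points | 116/166: 14.46 points | 1.02 |
| 80% | 128/160: 12.94 points | 133/166: 12.67 points | 1.02 |
| 90% | 144/160: 9.91 points | 149/166: 9.81 points | 1.01 |

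**5. If 2090 and 2100 are applied across endpoints**

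Every loss between the IgA sample and Visit 7 would then count: 40 × 1.5/3.5 = 17.1 in Staggered and 40 × 1.0/3.5 = 11.4 in Co-administration. The comparison sets become about 177 and 171, with widths at 80% of 12.24 and 12.48 points. The ratios are 12.94/12.24 = 1.06 and 12.94/12.48 = 1.04.

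**The case against.** **Endpoint-specific use may be intended.** Section 6.1.3 refers back to Section 3, which has separate polio and IgA bullets. The same list holds code 2020 (baseline IgA at or above 20 U/mL, or unknown), which has no evident bearing on polio. Protocol 9.2.1 says only that participants may be eliminated. This is a fair reading of intent and lowers the weight of the point. But the intent is not written, and the common conditions of Table 2 still bind the IgA set to the full schedule. In an open-label trial the choice should not be left to discretion.

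**The Exposed Set analysis partly covers it.** SAP Table 2 adds that analysis if 5% or more of vaccinated participants with serological results are excluded in any group, and SAP 6.1.1 tabulates exclusions by reason. The data would then be reported. But the trigger is conditional (about 6 of 200 is 3%, below it unless other exclusions add up), and the Exposed Set also readmits out-of-window samples and incomplete Rotarix dosing. It does not give the IgA set that is wanted.

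**A reader might infer larger losses**, of about 17 and 11 infants with CIs 6% and 4% wider. The documents do not support this as the general case. A visit missed after IPV Dose 3 does not trigger 1070, 1040 or 2040, and those counts need 2090 or 2100 to cross endpoints.

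**A reader might also infer a biased comparison between groups.** Protocol 9.3.2 declines any IgA ratio or difference because the Rotarix schedule already differs by group, and SAP 4.3.2 plans none. Nothing in the documents links a missed IPV Dose 3 to the IgA response.

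**Conclusion.** The point holds on the text. One undivided PPS, with codes reaching to IPV Dose 3 and Visit 7, removes infants whose IgA endpoint was already complete and valid. The effect is modest: about 6 infants in Staggered and almost none in Co-administration from code 1070 alone, or a CI about 2% wider at an assumed 80% seroconversion. This rests on even accrual of the planned 20% losses, on each Visit 5 to Visit 6 loss being a missed dose, and on borrowing 160 as the IgA set size. Removals under 1040, 2040, 2070 and 2080 come on top and cannot be sized from the documents. Code 2070 is the one that could select on response, in an upward direction and by an unknown amount.

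The consequence is confined to secondary, descriptive endpoints. The primary polio test and its power are unaffected. The change is still worth making, because these are the trial's only rotavirus immunogenicity results and the loss is avoidable.

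**What to change.** State for each elimination code in SAP 6.1.3 which endpoint it applies to. For the anti-RV IgA PPS, count only deviations up to the post-Dose 2 IgA sample (Visit 5 in Staggered, Visit 6 in Co-administration):
- **1070 and 2080**: require the two Rotarix doses and only those IPV doses due before that sample.
- **1040, 2040, 2070 and the Visit 7 footnote on immune conditions**: end at that sample.
- **2090 and 2100**: apply to the IgA samples only.

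Keep the polio PPS running to Visit 7. Editing the codes alone is not enough, because the schedule requirement and the Visit 7 footnote are common conditions in SAP Table 2 and Protocol Table 15. Align both tables, and record the change in SAP 4.8, which now states that there are none.

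Cost: wording in the SAP and the protocol table, one extra PPS flag, and IgA and polio sets of different sizes. No new data and no change in sample size.
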